#### 7.1.4. Follow-up Period (Days 6 to 28)

All study assessments during the Follow-up Period are detailed in the SoA (Appendix 1).

Follow-up visits will occur 4, 9, and 23 days (study Days 9, 14, and 28 [end-of-study; EOS]) after the last dose of study drug for all subjects including those who discontinue treatment early (before completing 5 days of dosing). The eCOA eDiary device should be returned to the site on or before Day 14 (or post-treatment visit 2 [PT2]).

The Day 28 (EOS Visit) is a follow-up visit for post-treatment safety assessments and may be conducted as a telephone call.

Any subject with ongoing AEs/SAEs at the EOS Visit should be followed up until resolution of their AE/SAE or until the Investigator has determined that the event has stabilized as discussed in Section 9.3.

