# 7.3.2. Procedures for Early Discontinuation of Treatment or Early Discontinuation of Study

Subjects who discontinue treatment early (before completing 5 days of dosing) should return to the study site within 24 hours after the last dose of study drug for an EOT visit. Subjects should then return to the site 4 and 9 days (PT1 and PT2 visits) after discontinuation of study drug for post-treatment follow-up visits. A follow-up visit for post-treatment safety assessments also needs to be scheduled (23 days after study drug discontinuation) and may be conducted as a telephone call.

Subjects who discontinue the study early (before Day 28) should return to the study site within 24 hours if possible and no more than 48 hours later to complete the EOS procedures and return eCOA handheld device per the SoA (Appendix 1). Any subject who withdraws with ongoing AEs/SAEs should be followed up until resolution of their AE(s) or until the Investigator has determined that the AE(s) has stabilized.

Site staff will attempt to contact any subject's caregiver who does not return to the site for the EOT or EOS Visit at least 3 times using the caregiver preferred method of communication,

Clinical Study Protocol
EDP 938-201

followed by a letter requiring delivery notification if the 3 attempts were unsuccessful. Any subject who still cannot be reached following those attempts will be considered lost to follow-up. These subjects will be included in the PK and safety analysis as indicated in Section 11.2.

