#### 8.10.2. Parent/Guardian ReSVinet Clinical Scoring System and Palatability Question

During the study, subjects' parent(s)/guardian(s) will assess the severity of RSV-related signs and symptoms and complete the required response in the Parent/Guardian ReSVinet clinical scoring system using a handheld eCOA eDiary. They will also assess the palatability of study drug. A copy of the scoring system and the palatability question is provided in Appendix 3.

The eCOA eDiary will be provided to the parent(s)/guardian(s) on Day 1, and the Investigator/study site personnel will instruct the parent(s)/caregiver(s) on the completion of the eCOA eDiary. The eCOA eDiary should be returned to the study site at the Day 14 visit (or PT2).

On Day 1, the ReSVinet Scoring System assessment should be completed before administration of the first dose of study drug. Subsequently the eCOA eDiary should be completed predose QD each day through Day 14 and at approximately the same time each day  $\pm 2$  hours. The palatability question should be completed as soon as possible after each dose of study drug is administered.

The eCOA eDiary will automatically record the date and time of the eCOA assessments. Entries should be recorded by the caregiver at approximately the same time each day. Whenever possible, the same parent/caregiver should complete the eCOA eDiary and should be the primary caregiver of the child who has sufficient opportunity to notice or observe the signs and symptoms being evaluated in the eCOA eDiary. Study site personnel will review the completion of the parent/caregiver eCOA on a regular basis to ensure that the eCOA eDiary is completed correctly and on schedule to avoid missing or incorrect data. If a caregiver is unable to use the eDiary, a paper diary may be used.

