  - This analysis includes subjects who are hospitalized at randomization and required mechanical ventilation at any time after the first dose of study drug. The duration of mechanical ventilation (days) is defined as the sum of each duration of mechanical ventilation (days) that occurred from the first dose of study drug to the end of study. The duration of mechanical ventilation for the initial hospitalization is calculated as date/time of the end of mechanical ventilation date/time of first dose of study drug. The duration of mechanical ventilation for subsequent rehospitalization(s) is calculated as date/time of the end of mechanical ventilation date/time of the start of mechanical ventilation. Missing start times will be imputed to 00:01. Missing end times will be imputed to 23:59.
- Time to hospitalization for initial outpatients who are subsequently hospitalized
  - Time to hospitalization for initial outpatients who are subsequently hospitalized will be calculated, defined as the time between the date/time of first dose to the first date of hospitalization.
- Time to resolution of symptoms for outpatients who are not hospitalized
  - Time to resolution of symptoms for outpatients at randomization who are not hospitalized during study, is defined as the time between the date/time of first dose to the first of 2 consecutive time points where each of the seven symptoms assessed by the Parent/Caregiver ReSVinet clinical scoring is 0 or 1. If a subject meets the resolution

definition (0 or 1 score for 2 consecutive timepoints) at baseline and Day 2, then this subject will be excluded from the analysis.

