# For continuous endpoints with multiple timepoints:

Absolute change from baseline in the outcome of interest (outcome variable) will be analyzed using a mixed-effect model for repeated measures (MMRM) to compare EDP-938 and Placebo.

The model includes treatment group (EDP-938, placebo) and Day (all scheduled post-baseline timepoints available) as fixed effect, associated baseline (as appropriate), and treatment group-by-Day interaction term as factors. Treatment groups will be compared at scheduled post-baseline timepoints of interest. An unstructured covariance matrix will be imposed. If the unstructured covariance matrix fails to converge, then the following covariance structure will be assessed in this order: autoregressive, compound symmetry, Toeplitz. The Satterthwaite approximation will be used to estimate the denominator degrees of freedom. The least-squares means and two-sided 95% CIs of absolute change from baseline at each post-baseline timepoint will be derived via this model. The least-squares means and two-sided 95% CIs of AUC through Days 3, 5, 9 and 14 will be presented for individual groups and the difference between groups. The p-value will be presented for the difference between treatment groups at each post-baseline timepoint.

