# For time to event endpoints:

Kaplan-Meier estimates will be provided including at least median survival and its 95% CI on the combined EDP-938 and placebo for Parts 1 and 2. Kaplan-Meier plots will also be provided. Generalized Wilcoxon test will be performed to compare the EDP-938 vs Placebo. If appropriate, log-rank test will be performed as well. If required, a Cox proportional hazards model, adjusting for associated baseline assessment (if appropriate), would be considered. Subjects who did not achieve the specified event will be censored as follows:

RSV RNA viral load:

• Subjects who have not been followed through the Day 14 visit (discontinued from the study or incomplete follow-up) or completed Day 14 visit will be censored at Day 14 visit date.

Parent/Guardian ReSVinet, Professional ReSVinet, Parent/Guardian RESOLVE-P, Caregiver Global Impression of Severity (CaGI-S), Caregiver Global Impression of Change (CaGI-C):

• Subjects who have not been followed through the Day 14 visit (discontinued from the study or incomplete follow-up) or completed Day 14 questionnaire will be censored at Day 14.

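### The eDiary can be handed back before the daily caregiver ReSVinet entries due through Day 14 are complete, and the pooled time-to-event rule still carries such a child to Day 14

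*Protocol*

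**What the plan says.** - **Entries due.** Protocol 8.10.2: "Subsequently the eCOA eDiary should be completed predose QD each day through Day 14". The Schedule of Assessments likewise asks for 14 days of once-daily entries.
- **Device return.** Protocol 7.1.4: "The eCOA eDiary device should be returned to the site on or before Day 14", with PT2 as the alternative and no earliest day. Protocol 8.10.2 places return at the Day 14 visit or PT2. The two rules differ, and neither ties return to completion of the last entry.
- **Visit timing.** The Schedule of Assessments sets PT2 at Day 14 ± 2. For children who stop dosing early, Protocol 7.3.2 says: "Subjects should then return to the site 4 and 9 days (PT1 and PT2 visits) after discontinuation of study drug".
- **Back-up.** Protocol 8.10.2 allows a paper diary for caregivers who cannot use the eDiary. Nothing says how entries continue once the device has gone back.
- **SAP mapping.** SAP 4.5 gives site-visit measures a Day 14 window of Days 12 to 16, but assigns diary data by exact study day. SAP 4.3 generally does not impute missing data.
- **SAP endpoint.** In SAP 4.13.4, symptom resolution is dated to the "first of 2 consecutive time points where each of the seven symptoms assessed by the Parent/Caregiver ReSVinet clinical scoring is 0 or 1". The endpoint covers children who are outpatients at randomization and are not hospitalized during the study.
- **SAP censoring.** In the pooled time-to-event analysis (SAP 4.13.5), a child without the event who was not followed through the Day 14 visit or "completed Day 14 questionnaire will be censored at Day 14".

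**The concern.** A site that follows the return wording to the letter can take the device away while required entries are still outstanding. Because the visit window is two-sided and the diary has no analysis window, an entry on Day 12 or 13 cannot stand in for Day 14. The two-entry rule extends the effect back by one day: the last entry can confirm an earlier resolution but cannot begin a new one.

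At stake are the end-of-diary results for caregiver ReSVinet. These are the secondary endpoint of time to symptom resolution in outpatients who are not hospitalized, and the ReSVinet change, AUC and time-to-resolution summaries in the steroid and coinfection analyses of SAP 4.13.6. Under the pooled censoring rule, days with no possible observation are counted as days at risk and unresolved.

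**Working it through.** **Inputs.** Entries due on Days 1 to 14 (Protocol 8.10.2). PT2 at Day 14 ± 2 (Schedule of Assessments). PT2 nine days after the last dose for early discontinuers (Protocol 7.3.2). Five dosing days. Two consecutive qualifying entries for resolution (SAP 4.13.4). The distribution of PT2 days is not given, so it is varied below.

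**Reproducing the plan's window.** 14 − 2 = 12 and 14 + 2 = 16. This matches the Days 12 to 16 in SAP 4.5 for site-visit measures.

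**Entries lost per child.** Let R be the return day, and assume that the entry for day R is made before hand-back. Entries lost = max(0, 14 − R).

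- Dosing completed, device returned at PT2: R = 12 loses 2 of 14; R = 13 loses 1; R = 14 to 16 loses none.
- Dosing stopped early, last dose on day L: nominal PT2 = L + 9. A last dose on Day 5 gives 5 + 9 = 14, the labelled day. L = 1, 2, 3, 4 gives Day 10, 11, 12, 13, and return then loses 4, 3, 2, 1 entries. If the ± 2 window also applies to this shifted date, the earliest return is L + 7 (Day 8, 9, 10, 11), which loses 6, 5, 4, 3.

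**Coverage on a given day.** Coverage on day d = share of children with R ≥ d. Every row is an assumption.

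| Assumed return days | Day 13 | Day 14 |
|---|---|---|
| All on Days 14 to 16 | 100% | 100% |
| Weights 1:2:3:2:1 over Days 12 to 16 | 8/9 = 89% | 6/9 = 67% |
| Even over Days 12 to 16 | 4/5 = 80% | 3/5 = 60% |
| Even over Days 12 to 14 | 2/3 = 67% | 1/3 = 33% |
| All on Day 12 | 0% | 0% |

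If the entry for the return day is not made, the even spread over Days 12 to 16 gives 60% on Day 13 and 40% on Day 14.

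**Confirmable resolutions.** A resolution starting on day k needs entries on k and k + 1, so it can be confirmed only if R ≥ k + 1. Under the even spread over Days 12 to 16, starts on Day 11, 12 and 13 are confirmable in 100%, 80% and 60% of children. A start on Day 14 cannot be confirmed in any child, because the diary ends there.

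**What the SAP does with the gap.** Take a child returning the device on Day 12 without a confirmed resolution. In the descriptive summary of SAP 4.13.4, which uses non-missing values, the child contributes no time. In the pooled time-to-event analysis, the child is censored at Day 14, two days after the last entry.

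**With the device kept.** If it stays until the Day 14 entry is made, possible coverage on Days 13 and 14 is 100% under every row.

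**The case against.** The strongest reply is that the wording permits a loss without requiring one. Section 8.10.2 governs the diary, asks for entries through Day 14 and has site staff review completion regularly. Day 14 is the target and ± 2 only a tolerance. Read this way, 7.1.4 is a loose logistics sentence. That stands for children who complete dosing: a PT2 on Days 14 to 16 need lose nothing.

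Two further points also stand. The scope is narrow: the primary viral-load endpoint, the Professional ReSVinet scored at site visits and the RESOLVE-P completed on paper are untouched. The planned methods also soften the effect. For device returns on Days 12 to 16, resolutions starting before Day 12 are still seen. The generalized Wilcoxon test gives late events least weight. SAP 4.13.2, to which the caregiver AUC refers, includes a version scaled by 14 over the last observed time, although that assumes the earlier level continues.

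A reader might infer that late resolutions will be undercounted by some known share, or that the treatment comparison will be biased. The documents support neither. They give no visit-day distribution and no estimate of how many children first resolve on Days 12 or 13. A child who meets the definition on Day 12 and returns the device on Day 13, after that day's entry, is scored. Loss that follows clinic scheduling in a double-blind trial gives no reason to expect a difference between arms. Loss that follows early discontinuation could differ between arms, but no discontinuation rates are given.

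The reply does not dispose of early discontinuers. The protocol and its schedule label PT2 as Day 14, but nine days after the last dose is Day 14 only when the last dose was on Day 5. For these children an on-schedule return at PT2 does lose entries.

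**Conclusion.** The point holds as an internal conflict with a limited reach. The protocol requires entries through Day 14 and allows the device to leave before then: up to two entries early for children completing dosing who return it at PT2, and four to one early for discontinuers who return it at nominal PT2. The SAP does not absorb the gap, because diary days are exact, resolution needs two consecutive entries and pooled censoring is fixed at Day 14.

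The size cannot be settled from the documents. Day 14 coverage runs from 100% to 0% depending on return days; 80% on Day 13 and 60% on Day 14 illustrate one assumed spread and are not forecasts. These are coverage figures, not estimates of bias. They assume that the entry is made on the day of return and that no paper diary takes over. How far the pooled time-to-event method reaches the outpatient endpoint is also not fully visible: SAP 4.13.5 names caregiver ReSVinet in its censoring rule but refers to Section 4.13.7, which is not in the available text.

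This is a cheap improvement to the last days of a secondary and supporting instrument. It does not threaten the primary analysis.

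**What to change.** 1. Align Protocol 7.1.4 and 8.10.2 so that the device is kept until the Day 14 entry has been made, whatever the day of PT2, and say that this includes children who stop dosing early. Drop the 7.1.4 wording that lets it come back before then.
2. Where the device has to be returned at an earlier PT2, have the remaining days completed on the paper diary, and extend the 8.10.2 permission to cover this case.
3. In SAP 4.13.5, censor caregiver ReSVinet time-to-event data at the last diary entry when entries stop before Day 14. A complete diary is already censored at its last entry, so this applies the same convention to a short one.

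The cost is a small wording change in each document, and some later device returns or a few paper pages.

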# 7.2. Addition or Replacement of Subjects

If the objectives of the study are not met (due to subject dropout, lack of sufficient data points, or other reason) or based on recommendation from the SSC, additional subjects may be enrolled. Subjects who withdraw from the study before receiving the first dose of study drug may be replaced. Subjects who withdraw from the study after receiving the first dose of study drug will not be replaced, except as recommended by the SSC.

# 7.3. Subject Withdrawal/Early Termination

Subjects may be withdrawn at any time at the request of their caregiver(s) or at the discretion of the Investigator or Enanta Pharmaceuticals, Inc. for safety, behavioral, or administrative reasons. However, the Investigator should consult with the subject where possible before prematurely removing a subject. For any subject who is withdrawn by their caregiver, the Investigator should inquire about the reason for withdrawal, request that the subject's caregiver returns all unused investigational product(s), request that the subject returns for the EOT, PT1, and PT2 visits ( $\leq$ 24 hours after last dose, 4, and 9 days after last dose) (if applicable) and the EOS Visit, and follow-up with the subject's caregiver regarding any unresolved AEs. If a subject's caregiver withdraws from the study and also withdraws consent for disclosure of future information, no further evaluations should be performed, and no additional data should be collected. Enanta Pharmaceuticals, Inc. may retain and continue to use any data collected before such withdrawal of consent.

#### 7.3.1. Withdrawal Criteria

Subjects may be discontinued from the study at any time if the subject's caregiver, Investigator, or Sponsor determines that it is not in the best interest of the subject to continue participation. Reasons for discontinuation include the following:

- AE;
- Lack of efficacy;
- Lost to follow-up;
- Withdrawal by subject;
- Protocol deviation (including noncompliance with study drug or study procedures);
- Study terminated by the Sponsor;
- Other.

# 7.3.2. Procedures for Early Discontinuation of Treatment or Early Discontinuation of Study

Subjects who discontinue treatment early (before completing 5 days of dosing) should return to the study site within 24 hours after the last dose of study drug for an EOT visit. Subjects should then return to the site 4 and 9 days (PT1 and PT2 visits) after discontinuation of study drug for post-treatment follow-up visits. A follow-up visit for post-treatment safety assessments also needs to be scheduled (23 days after study drug discontinuation) and may be conducted as a telephone call.

Subjects who discontinue the study early (before Day 28) should return to the study site within 24 hours if possible and no more than 48 hours later to complete the EOS procedures and return eCOA handheld device per the SoA (Appendix 1). Any subject who withdraws with ongoing AEs/SAEs should be followed up until resolution of their AE(s) or until the Investigator has determined that the AE(s) has stabilized.

Site staff will attempt to contact any subject's caregiver who does not return to the site for the EOT or EOS Visit at least 3 times using the caregiver preferred method of communication,

Clinical Study Protocol
EDP 938-201

followed by a letter requiring delivery notification if the 3 attempts were unsuccessful. Any subject who still cannot be reached following those attempts will be considered lost to follow-up. These subjects will be included in the PK and safety analysis as indicated in Section 11.2.

### 7.3.3. Documentation of Withdrawal of Subjects

The reason for early withdrawal/termination/lost to follow-up of any subject from the study must be documented on the appropriate eCRF. If the reason for early withdrawal is an AE or an abnormal laboratory value, the specific event or test result, if available, should be recorded on the AE eCRF and the subject should be monitored until the event is resolved or deemed stable by the Investigator.

# 8. STUDY PROCEDURES/EVALUATIONS

## 8.1. Timing of Assessments

The timing of assessments is shown in the SoA (Appendix 1). If multiple assessments are scheduled for the same timepoint, it is recommended that noninvasive procedures being done before more invasive procedures, eg, first complete and ReSVinet Scoring System (parent/guardian on ReSVinet eCoA and clinician scoring could be concurrent), then ECG, then vital signs/SpO2, then nasal swab, and finally blood draw.

# 8.2. Demographics and Medical History

Demographics and baseline characteristics including age (months and days), gestational age (in weeks), gender or sex, race, ethnicity, and medical history will be obtained from each subject and entered in source documents and either interactive response technology (IRT) or eCRFs as reported during Screening. Significant medical history including surgeries will be obtained by consulting with the subject's caregiver. As a rule, all medical events occurring within the last 6 months should be recorded. For events that occurred more than 6 months before Screening (and that are not ongoing), only significant or relevant events should be entered on the eCRF. Any items in the history that are still ongoing should be noted as such in the eCRF.

If there is a question concerning a subject's medical history, then medical records may be requested from the subject's primary care physician, as appropriate.

# 8.3. **Prior and Concomitant Treatment**

Medications taken within 1 month of signing the ICF, blood products administered within 6 months of study drug administration, and medications taken during the study will be recorded with indication, dosage, route of administration, and start and stop dates of administration. Only relevant medications and therapies should be recorded if they were discontinued more than 1 month before signing the ICF (see Section 5.8). Subjects' caregivers will be questioned about concomitant medication at each study site visit. Concomitant therapies will be collected from the time of consent. This will include requirement for hydration and feeding by intravenous (IV) catheter/nasogastric tube and requirement for and duration of oxygen supplementation/noninvasive mechanical ventilation support.

# 8.4. Vital Sign Measurements

Vital signs include heart rate, respiratory rate, systolic and diastolic blood pressure, body temperature, and pulse oximetry (to measure peripheral capillary oxygen saturation [SpO2]).

# 8.5. Electrocardiograms

ECGs will be performed locally. A standard bedside 12-lead ECG machine that calculates heart rate and measures PR, QRS, QT, RR, and QT interval corrected for heart rate according to Fridericia (QTcF) intervals is strongly preferred but in cases where a 12-lead ECG is not possible or feasible, a 6-lead ECG may be used.

During the collection of ECGs, subjects should be calm, resting quietly, or sleeping if possible. If blood sampling and a nasal swab are scheduled for the same timepoint as ECG recording, those assessments should be done after the ECG.

The Investigator or designee should review the ECG for gross abnormalities and interval measurements of concern (absolute readings). The clinical interpretation by the Investigator or designee of the ECGs should be recorded on a hard copy of the ECG (ie, clinically significant or not clinically significant).

An ECG may be repeated at the discretion of the Investigator to address suspected errors in performance. Before dosing, the screening ECG must be reviewed to confirm that no clinically significant cardiac abnormalities are present.

All subjects with new abnormal cardiac laboratory values or abnormal ECG results after receiving study drug should have echocardiograms. For echocardiogram results, only clinically significant abnormalities should be recorded as AEs.

